#### Conceptual Model for Project POINT

recovery coach offers the patient a range of evidence-based services including a brief assessment of high-risk behaviors, Hepatitis C and HIV testing, harm reduction counseling informed by motivational interviewing, and treatment referrals with follow-up to either a MOUD provider, detoxification services, or an inpatient treatment setting—with most patients choosing MOUD referral. Patients are also offered a take-home naloxone kit (i.e., the overdose reversing drug, which is offered as part care delivered by the recovery coach) and assistance with Medicaid enrollment, if applicable. Close collaboration with the local community mental health provider ensures POINT patients have their first assessment for MOUD within 1-2 business days of ED discharge.

Grounded in the concept of critical time intervention, recovery coaches provide over the phone or in person support to navigate barriers to care throughout the recovery process. Recovery coaches also offer to accompany patients to intake appointments or criminal justice and child welfare meetings as part of the standard care they deliver. Recovery coaches reach out to the client every 2-3 days, initially, until the patient is successfully engaged in recovery services. The entire care transition process takes between 2 weeks and several months, and POINT leaves the door open so patients can re-engage at any point they require help overcoming recovery barriers. Recovery coaches do not collect data for study purposes during this time; rather, any information they collect will be solely for the purposes of providing professional care as a recovery coach.

The control condition refers to standard care within the ED, in which patients receive a list of available local treatment options for opioid use disorder.

---

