## 9 STATISTICAL CONSIDERATIONS

## 9.1 STATISTICAL HYPOTHESES

Primary Endpoint:

- Overdose Admissions
  - [Measured: 1 year pre-enrollment through 1 year post-enrollment]

We hypothesize that, compared to patients in the control condition, patients receiving the POINT intervention will experience fewer subsequent admissions to the ED for overdose.

Secondary Endpoints:

- MOUD Engagement
  - [Measured: 1 year pre-enrollment through 1 year post-enrollment]
- Duration of MOUD Engagement
  - [Measured: 1 year pre-enrollment through 1 year post-enrollment]
- ED Admissions
  - [Measured: 1 year pre-enrollment through 1 year post-enrollment]
- Inpatient Hospital Admissions
  - [Measured: 1 year pre-enrollment through 1 year post-enrollment]
- Time to Relapse
  - [Measured: Enrollment through 1 year post-enrollment]
- Medicaid Enrollment for Participants Without Insurance
  - [Measured: Enrollment through 1 year post-enrollment]
- Child Welfare Involvement
  - [Measured: 3 years pre-enrollment through 1 year post-enrollment]
- Incarceration
  - [Measured: 3 years pre-enrollment through 1 year post-enrollment]

We hypothesize that, compared to patients in the control condition, patients receiving the POINT intervention will experience better recovery outcomes (i.e., higher MOUD engagement and longer duration of engagement, lower ED and inpatient admissions, longer times between relapse, higher Medicaid enrollment for those without insurance, lower child welfare involvement, and lower incarceration).

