### 9.4 STATISTICAL ANALYSES

#### 9.4.1 GENERAL APPROACH

We will summarize patient characteristics using means and standard deviations for continuous variables and counts and proportions for categorical variables. Initial analysis of outcomes (using data pulled at 9 months) will focus on MOUD engagement one-month post overdose, as all other outcomes will be too distal to observe any meaningful change. This time period is based on our prior POINT experience demonstrating initial engagement tends to happen within 1-2 weeks of overdose. We will focus on immediate outcomes (e.g., treatment engagement, length, dropout). While observed change in more distal outcomes (e.g., subsequent overdose and mortality) is unlikely to be seen in such a short pilot period, we will look at them and, if needed, adjust the benchmark (established based on our experience at Eskenazi) for the power analysis. Summary of outcome measures will be computed similarly. The 95% confidence intervals of outcome measures for the POINT and standard care arms will be used to estimate the rate of binary outcomes and mean of continuous outcomes.

The primary analysis involves comparison of outcome measures post ED discharge between the POINT and standard care arms. Binary outcome measures (e.g., MOUD engagement and dropout, subsequent overdose, overdose mortality, and all-cause mortality) will be compared between the POINT and standard care arms using the Fisher's exact test. Length of MOUD treatment will be compared using the Wilcoxon rank sum test. Comparison of the length of time to relapse will be conducted using the survival analysis. Time to relapse will be plotted using the Kaplan Meier curve and comparison between the POINT and standard care arms will be performed using the log rank test.

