The secondary analysis involves comparing outcome measures pre- and post-ED discharge for POINT patients. Binary outcomes including child welfare involvement will be compared using the McNemar's test and the continuous outcome including the days of incarceration will be compared using the Wilcoxon signed rank test due to the skewness of the data. Additional analyses will be conducted to account for patient characteristics in the comparison between the POINT and standard care arms using logistic regression for binary outcomes, Poisson regression for length of MOUD treatment, and Cox proportional hazards model for time to relapse. For the comparison pre- and post-ED discharge in the POINT arm, generalized estimating equations approach will be performed using logistic regression for Medicaid enrollment and child welfare involvement and Poisson regression for days of incarceration. Hospitals will be included in the models as a fixed effect to account for the potential differences in patient population across hospitals.

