#### 9.4.3 ANALYSIS OF THE SECONDARY ENDPOINT(S)

Secondary endpoints	
Note if analysis of secondary endpoint(s) are dependent on findings of primary endpoint	Analysis of secondary endpoints are not dependent on the findings of primary endpoint.
Describe how each secondary endpoint is calculated, if not readily apparent	
Change in MOUD Engagement: Using state methadone treatment data, Medicaid claims data, state prescription drug monitoring data, and electronic health records data to identify whether or not the person engaged in at least one episode of MOUD treatment (methadone, buprenorphine, or naltrexone) within the specified time period.
 
Change in MOUD Engagement Duration: Using state methadone treatment data, Medicaid claims data, state prescription drug monitoring data, and electronic health records data to calculate the number of days MOUD treatment was received during the specified time period.
 
Change in ED Admissions: Using electronic health records, it is calculated as the total combined number of all-cause ED presentation within the specified time period.
 
Change in Inpatient Hospital Admissions: Using electronic health records, it is calculated as the total combined number of all-cause hospital admissions within the specified time period.
 
Time to Relapse: Using electronic health records data, it is calculated as number of days to the first overdose ED visit or overdose death since the index ED. Subjects who did not experience overdose ED or overdose death are censored at the end of the specified time period or the time of death due to other reasons, whichever occurred first
 
Change in Medicaid Enrollment for Participants Without Insurance: Using Medicaid claims data to identify Medicaid coverage among participants within the specific time period.

	
Change in Child Welfare Involvement: Using child welfare data to identify the number of new cases and children removed from the home within the specified time period.
 
Change in Incarceration: Using public incarceration data to identify the number of days of incarceration within the specific time period.

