
Describe the scale (nominal/binary/categorical, ordinal, and interval); state if it is measured as a single endpoint/summary measure or repeated measure
	
Change in MOUD Engagement: binary
 
Change in MOUD Engagement Duration: Interval/Ratio
 
Change in ED Admissions: binary
 
Change in Inpatient Hospital Admissions: binary
 
Time to Relapse: Interval
 
Change in Medicaid Enrollment for Participants Without Insurance: Binary
 
Change in Child Welfare Involvement: binary
 
Change in Incarceration: Interval

Describe the statistical procedure(s) that will be used to analyze the secondary endpoint (e.g., multiple regression, mediation or moderation analyses, multilevel modeling, MANOVA). Describe the covariates and factors in the model. Provide rationale for covariates and how they will be selected to achieve a parsimonious model. If decision to specify covariates is deferred for the SAP, indicate here.
	
We will summarize patient characteristics using means and standard deviations for continuous variables and counts and proportions for categorical variables. The primary analysis involves comparison of outcome measures post ED discharge between the POINT and standard care arms. Binary outcome measures (e.g., MOUD engagement, subsequent overdose, overdose mortality, and all-cause mortality) will be compared between the POINT and standard care arms using the Fisher's exact test. Length of MOUD treatment will be compared using the Wilcoxon rank sum test. Comparison of the length of time to relapse will be conducted using the survival analysis. Time to relapse will be plotted using the Kaplan Meier curve and comparison between the POINT and standard care arms will be performed using the log rank test.

Describe how results of statistical procedure(s) will be presented (e.g., adjusted means (Least-squares means (LSMEANS)) with standard errors or effect size
	
For continuous endpoints, we will present the mean and standard deviation or median and interquartile range for each treatment arm.

	Frequency and percentages are presented for binary endpoints. Time to event endpoints are presented using estimated survival probability at the end of the specified time period.

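### The child welfare endpoint is scored from new events, so a case already open at enrollment counts as no involvement and its closure cannot show as a benefit

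*Combined protocol and SAP*

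**What the plan says.** Section 9.1 hypothesises better results with POINT than control, including "higher Medicaid enrollment for those without insurance, lower child welfare involvement, and lower incarceration". The child welfare window is given as "Measured: 3 years pre-enrollment through 1 year post-enrollment".

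Section 9.4.3 gives the derivation: "Using child welfare data to identify the number of new cases and children removed from the home within the specified time period". The scale row reads "Change in Child Welfare Involvement: binary". The step from count to yes/no is not written, but a count of zero can only become 'no'.

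Section 9.4.1 sets the period for the comparison of arms: "The primary analysis involves comparison of outcome measures post ED discharge between the POINT and standard care arms". It assigns binary outcomes to Fisher's exact test. It then adds a pre/post analysis within the POINT arm: "Binary outcomes including child welfare involvement will be compared using the McNemar's test".

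Two neighbouring definitions in 9.4.3 work differently. Incarceration is derived by "Using public incarceration data to identify the number of days of incarceration within the specific time period", and Medicaid enrollment by coverage within the period. Both pick up a state that began before the window.

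The intervention description in Section 6.1.1 says: "Recovery coaches also offer to accompany patients to intake appointments or criminal justice and child welfare meetings as part of the standard care they deliver".

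**The concern.** The name and the hypothesis refer to a state, being involved with the child welfare system. The derivation counts events that start inside the window. A participant who already has an open case is in that state from the first day of follow-up, yet adds nothing to the post-enrollment count unless something new happens.

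Such participants are among those for whom a coach's attendance at child welfare meetings could matter. If POINT helps to close existing cases, the planned comparison of arms cannot detect it. A null result could then be reported as no effect on child welfare involvement, when ongoing involvement was never measured.

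**Working it through.** **The rule applied to four hypothetical participants (post-enrollment year)**

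| Participant | New cases | Removals in window | Score |
|---|---|---|---|
| A: case opened and child removed 6 months before enrollment, both unresolved at month 12 | 0 | 0 | no |
| B: as A, but case closed and child returned at month 3 | 0 | 0 | no |
| C: never involved | 0 | 0 | no |
| D: new case, closed within a month | 1 | 0 | yes |

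A, B and C cannot be told apart, and D scores worse than A. The zeros for new cases follow from the text. The zeros for removals in A and B read a removal as one dated inside the window.

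**How many participants could be affected**

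The documents give no child welfare figures. The only sizing figure, 356 per arm in Section 9.2, concerns the primary endpoint and does not enter here. Assume a low, steady onset rate r per year and exponential case lengths with mean L years.

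- Open at enrollment: about rL. New in the year: about r. Open at some time in the year: about r(1 + L).
- Share of those involved who have no new case: rL / [r(1 + L)] = L/(1 + L).
- Share of those involved whose case is open all year: L/(1 + L) × exp(−1/L).

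| L (years) | No new case | Open all year |
|---|---|---|
| 0.5 | 33% | 0.333 × 0.135 = 5% |
| 0.75 | 43% | 0.429 × 0.264 = 11% |
| 1 | 50% | 0.500 × 0.368 = 18% |
| 1.5 | 60% | 0.600 × 0.513 = 31% |
| 2 | 67% | 0.667 × 0.607 = 40% |

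Simulation with r = 0.06 gave 32%, 43%, 51%, 60% and 67% for the first share. At L = 1, about 11% of participants were involved during the year and about 5.5% had a new case.

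**What the comparison of arms would miss**

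Assume that a share o of each arm has a case open at enrollment, that all of these stay open for 12 months under control, and that POINT closes half of them at month 3. New-event rates are equal. The mean saving in open-case time is (o/2) × (12 − 3) months per participant:

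- o = 5%: 0.225 months
- o = 10%: 0.45 months
- o = 20%: 0.90 months

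Against o × 12 months under control, this is ½ × 9/12 = 37.5% less time in existing cases. The new-event rule shows a difference of zero.

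**The pre/post test**

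Participant A moves from 'yes' before enrollment to 'no' after it, with no change in status. This need not tilt McNemar's test. With equal 1-year windows and steady onset (r = 0.06), pre-only and post-only pairs per 300 participants were 16.6 v 16.5, 16.3 v 16.3, 16.3 v 16.2, 16.0 v 16.1 and 15.6 v 15.7 over the five values of L.

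A tilt does appear with the 3-year and 1-year windows. Let a = 1 − exp(−3r) and b = 1 − exp(−r). The expected ratio of pre-only to post-only pairs is a(1 − b) / [(1 − a)b]. For r = 0.02, 0.05 and 0.10 it is 3.06, 3.16 and 3.33. That comes from window length and is a separate matter.

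**The case against.** Counting new events is a legitimate choice. It leaves out cases that POINT could not have caused, it resembles the plan's other event-based endpoints, and it is openly defined. Randomization should balance prior cases in expectation. All of this stands: the comparison of new events between arms is not invalid. What remains is that it answers a narrower question than the hypothesis asks, and the plan does not say so.

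The shares above rest on assumed rates and lengths. The model also ignores a removal inside the window during an older case, which the rule does count, and a second case opened while one is running. Both would lower the share missed.

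A reader might infer more than the documents support:

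- **That unresolved cases produce a false reduction in McNemar's test.** Six pairs all moving from yes to no give an exact p of 0.031, and ten give 0.002, but only if no new cases offset them. A net tilt needs onsets concentrated before enrollment, or the unequal windows.
- **That a third to two thirds of those involved have a case running all year.** That range covers every case open at enrollment with no new one, including cases that close in the first week. The whole-year share is about 5% to 40%.
- **That continuing placements are expressly excluded.** The wording on children removed can be read otherwise, and this needs to be settled.
- **That cases and children are added in a way that distorts the score.** For a yes/no outcome, any new case or removal gives the same result whether or not the counts are summed.

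**Conclusion.** The point holds as a mismatch between the endpoint's name and hypothesis on one side and its derivation on the other. Scoring an open case with no new event as not involved follows directly from the text. For placements it follows from the natural reading. The consequence is that closure of an existing case cannot appear in the comparison of arms.

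The size is uncertain. Under steady onset and mean case lengths of 0.5 to 2 years, about 33% to 67% of those involved in the year would be scored as not involved. These are illustrations, not estimates for this population. The documents do not support a claim that the rule by itself biases the pre/post test.

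Severity is minor. The endpoint is secondary in Sections 1.1 and 9.1 and exploratory in Section 3, and the primary result is untouched.

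**What to change.** In Section 9.4.3:

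1. Keep any new case or removal after enrollment as a named yes/no component. Write the yes/no rule, and say whether a removal must be dated inside the window.
2. Add the number of days with an open case or out-of-home placement in the post-enrollment year, compared between arms. This parallels the incarceration days already planned. A yes/no definition of open on at least one day would not be enough, because participants A and B would both score yes and the closure would still be hidden.
3. Adjust both measures for involvement at or before enrollment, using the 3-year pre-enrollment records already obtained under Section 8.1.

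If the extract has no end dates, rename the endpoint and the hypothesis as new child welfare case or removal, adjust for prior involvement, and draw no conclusion about ongoing involvement.

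The cost is SAP wording and a little programming. The days measure needs case and placement end dates, which the documents do not confirm are supplied. The renaming option needs none.

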### 7.3 LOST TO FOLLOW-UP

Study participants are involved in data collection activities at a single time (i.e., enrollment) and do not participate in any follow-up data collection. Participants of the intervention arm are not required to engage in further interactions with the recovery coach; thus, participants can disengage whenever they prefer.

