### 8.3.6 SERIOUS ADVERSE EVENT REPORTING

Serious adverse events will be reported to the IRB and NIDA Program Officer within 24 hours, and a written follow-up (including information on the date of the event, what occurred, actions taken by project staff, any planned follow up, the intervention group/study arm of the affected participant, whether the event appears to be related to the intervention) will be provided within 72 hours of the event. Confidentiality will be breached in any circumstance where mandatory reporting is required. We have put procedures in place with the social work staff at the hospital and will inform them when there are concerns of self-harm or child abuse/neglect. As this is a long-term follow-up study, we have no way of tracking a number of events that could happen.

If any adverse event is noted, we will immediately contact the IRB and inform the ED. Additionally, participant withdrawals or complaints will be monitored by [name] to ensure that study procedures have not resulted in unanticipated outcomes to participants. Results of all data safety and monitoring activities will be reported to NIDA annually. Subject withdrawals and complaints will be monitored by the PIs with assistance from the Project Manager to ensure study procedures designed to protect the privacy and confidentiality of participants are adequate and no unanticipated distress or unintended outcomes have resulted from any of the study procedures.

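### The child welfare endpoint merges new cases with removals, so closer observation in the POINT arm can raise it and be misread as worse recovery

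*Combined protocol and SAP*

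**What the plan says.** Section 9.4.3 calculates the endpoint by "Using child welfare data to identify the number of new cases and children removed from the home within the specified time period". The scale row of the same table reads "Change in Child Welfare Involvement: binary", so one new case is enough to make a participant an event. Section 9.1 gives the window as "Measured: 3 years pre-enrollment through 1 year post-enrollment" and hypothesises, for POINT, "higher Medicaid enrollment for those without insurance, lower child welfare involvement, and lower incarceration". The synopsis and section 9.1 list the endpoint as secondary; section 3 lists it as exploratory and expects it to improve as a result of treatment engagement.

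On reporting, section 8.3.6 states: "Confidentiality will be breached in any circumstance where mandatory reporting is required". It adds that the study team has procedures with hospital social work staff and "will inform them when there are concerns of self-harm or child abuse/neglect".

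On contact, section 6.1.1 says of the POINT arm: "Recovery coaches reach out to the client every 2-3 days, initially, until the patient is successfully engaged in recovery services". The process lasts from 2 weeks to several months, re-engagement stays open, and coaches offer to go with patients to child welfare meetings. Control patients receive a list of local resources (sections 4.1 and 6.1.1). Section 8.3.4 recognises that coaches may learn of adverse events in POINT participants during follow-up, and names no similar channel for controls.

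On analysis, section 9.4.1 names McNemar's test and a GEE logistic model for child welfare before versus after discharge within POINT. The between-arm test follows from the general rule in section 9.4.3 that binary variables are compared with Fisher's exact test.

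**The concern.** A new child welfare case depends on what happens in a family and on whether someone notices and reports it. Randomization balances the first at baseline. It does not balance the second, because the intervention itself adds weeks or months of contact with a coach. Section 2.1 rests the use of coaches on patients being more willing to share personal struggles with a peer.

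A removal is a later and more consequential step, and so less directly exposed to extra reporting, though not immune, since it can follow from a report. Merging the two lets the more exposed component drive the result. A true reduction could be masked, or an excess of new cases in POINT could be reported as families doing worse. The plan does not record who made a report, does not separate the components, and states no limitation for this endpoint.

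**Working it through.** **1. Do the passages support the mechanism?** The endpoint includes new cases (9.4.3). A reporting route exists (8.3.6). Planned contact after the index visit is described for POINT only (4.1, 6.1.1, 6.1.2). The step from a coach's concern after discharge to an opened case is inferred: section 8.3.6 speaks of social work staff at the hospital and does not say that the route is used during telephone follow-up. Concerns raised at the enrollment interview can arise in either arm and are taken as balanced.

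**2. The plan's own figure.** No rate or power is given for child welfare. The only sample size, 356 per arm (section 9.2), is for the primary endpoint. With 12% versus 6%, two-sided 5%, 80% power and mean rate 0.09:

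n = [1.96·√(2·0.09·0.91) + 0.8416·√(0.12·0.88 + 0.06·0.94)]² / 0.06² = 356 per arm.

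It reproduces, but bears on the child welfare point only as the planned n. Sections 1.2 and 9.2 say it was not reached.

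**3. Illustration.** Let p be the true control rate of any new case or removal, RR the true effect, and s the excess probability that coach contact leads to a case in a POINT participant who would otherwise have none. All three are assumptions, and the model takes no offsetting extra observation in controls.

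Observed POINT rate = p·RR + (1 − p·RR)·s

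With no true effect (RR = 1), the observed POINT-minus-control difference is (1 − p)·s:

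| p | s = 1% | s = 2% | s = 5% |
|---|---|---|---|
| 5% | +0.95 points | +1.9 | +4.75 |
| 10% | +0.9 | +1.8 | +4.5 |
| 20% | +0.8 | +1.6 | +4.0 |

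A true 25% reduction (RR = 0.75) is fully cancelled when s = 0.25p / (1 − 0.75p): 0.0125/0.9625 = 1.3% at p = 5%; 0.025/0.925 = 2.7% at p = 10%; 0.05/0.85 = 5.9% at p = 20%.

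**4. Effect on the test.** Exact enumeration of the two-sided Fisher test. First, a true halving from 10% to 5%, with power to show benefit:

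| s | Observed POINT rate | 356 per arm | 150 per arm (assumed) |
|---|---|---|---|
| 0 | 5.0% | 67.7% | 29.8% |
| 1% | 6.0% | 46.4% | 19.1% |
| 2% | 6.9% | 27.3% | 11.6% |
| 4% | 8.8% | 6.2% | 3.7% |

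Second, no true effect, with the chance of a significant result against POINT. At 356 per arm and a 6% control rate it is 1.7%, 5.4%, 13.1% and 41.0% for s = 0, 1%, 2% and 4%. At s = 4% it falls to 27.7% with a 10% control rate at 356 per arm, and to 16.7% with a 6% control rate at 150 per arm. The 4% column is an extreme: against a 6% base it adds 0.94 × 4% = 3.8 points across all participants, including any without children.

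**5. Within-POINT comparison.** Coach contact exists only after enrollment, so new cases in the post period are exposed in the same way. The unequal windows, 3 years before against 1 year after, pull in the opposite direction. The net effect cannot be stated.

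**The case against.** The strongest reply is that nothing is mismeasured. Outcomes come from the Department of Child Services for both arms (section 8.1). The trial is pragmatic and tests POINT as delivered, and coach contact is the intervention. A case opened after a coach's concern is a real consequence of offering POINT and belongs in the comparison of randomized arms. This stands. What remains is that section 3 presents the endpoint as a marker of recovery, and a case opened because someone was watching does not show worse recovery.

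A reader might infer that the endpoint is biased against POINT. The documents do not establish that. The route from coach to case after discharge is inferred, contact may be slight (section 4.3 accepts a single ED engagement, and section 6.1.2 ends attempts to reach a patient after two weeks without success), and section 2.2 describes the population as heavy users of hospital care, so controls may also come to the notice of hospital staff.

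A reader might also take section 7.3 to show that controls have no further contact. It says that participants "do not participate in any follow-up data collection", which concerns study data collection and covers both arms.

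Finally, it is tempting to log coach-raised concerns and drop the resulting cases. Section 6.1.1 says coaches collect no study data during follow-up, section 9.2 says the planned analyses have been conducted, and dropping post-randomization events almost entirely from one arm would favour POINT.

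**Conclusion.** The point holds as a matter of interpretation and reporting. The composite lets the component most open to detection stand for family outcome, in a trial where planned follow-up contact differs by arm. Coach-prompted reporting, taken alone, can only add cases in POINT, against the hypothesis; the net direction also depends on observation of controls, which the documents do not describe. The size cannot be computed from the documents. The illustrations show that an excess of about 1% to 6% would be enough to hide a true 25% reduction if control rates lie between 5% and 20% and controls have no offsetting observation. The primary endpoint is not affected, and no effectiveness claim depends on this endpoint.

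**What to change.** In section 9.4.3, replace the single yes/no outcome with two, each reported by arm with frequencies and percentages and compared with Fisher's exact test: any child removed from the home, and any new case. Apply the same split to the within-POINT pre/post analysis in section 9.4.1. State that removal is the component less exposed to detection, though not immune, and that an excess of new cases in POINT without an excess of removals will not be read as family harm.

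Only if the source and date of staff reports already exist in the data, add a supplementary result without those cases. Label it as a bound that favours POINT, not as a replacement for the comparison of all participants as randomized.

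The cost is a wording change and one additional unadjusted test on a non-primary endpoint; the definition already names both components. The multiplicity row of section 9.4.3, which says each endpoint is analysed once, should acknowledge the added test. The reporting duty in section 8.3.6 is unchanged.
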